2.1.2.3 EXPLORATORY ENDPOINTS

The following secondary endpoints will be derived:

- Time to start of symptoms (hours) = (datetime of first of two non-zero overall SSC scores within 2 consecutive days - challenge datetime)/(60*60)
 - Time will be rounded as detailed in section 5.3.4
 - Subjects not having at least two non-zero overall SSC scores (within 2 consecutive days) will be censored on the last evaluable SSC assessment
- Peak symptoms = highest overall SSC score
 - Pre-challenge time points will not be considered.
 - Peak overall SSC score will be rounded as detailed in section 5.3.4
 - Subjects not having at least two non-zero overall SSC scores (within 2 consecutive days) will be excluded from this analysis (peak symptoms not calculated).

	Statistical Analysis Plan	
FLU010	Final analysis	Final 3.0 of 15JUN2020

- Time to peak of symptoms (hours) = (datetime of highest overall SSC score - challenge datetime)/(60*60)
 - Time will be rounded as detailed in section 5.3.4
 - In case of identical peak values, the first in time will be considered.
 - Subjects not having at least two non-zero overall SSC scores (within 2 consecutive days) will be censored on the last evaluable SSC assessment
- Time to cessation of symptoms (hours) = (datetime of first zero overall SSC score following the last non-zero overall SSC score - challenge datetime)/(60*60)
 - Time will be rounded as detailed in section 5.3.4
 - Subjects not having at least two non-zero overall SSC scores (within 2 consecutive days) will be excluded from this analysis (time to cessation not calculated).
 - An event is defined as having two consecutive zero overall SSC scores not followed by a non-zero overall SSC score. Subjects without an event will be censored on the last evaluable SSC assessment.
- Time to feel well enough to go to work (hours) = (datetime of first positive answer (yes) following the last no answer - challenge datetime)/(60*60)
 - Time will be rounded as detailed in section 5.3.4
 - Subjects not having at least two negative answers (no) (within 2 consecutive days) will be excluded from this analysis (time to feel well enough to go to work not calculated).
 - Subjects having a negative answer as last assessment (including subjects not having any positive answer) will be censored on the last assessment.
- Duration of symptoms (hours) = (datetime of first zero overall SSC score following the last non-zero overall SSC score - datetime of first of two non-zero overall SSC scores within 2 consecutive days)/(60*60)
 - Pre-challenge time points will not be considered.
 - Duration will be rounded as detailed in section 5.3.4
 - Subjects not having at least two non-zero overall SSC scores (within 2 consecutive days) will be excluded from this analysis (duration not calculated).
 - The end of symptoms is defined as two timepoints with zero overall SSC score not followed by a timepoint with non-zero overall SSC score. If this does not occur, the end of symptoms will be set to the last evaluable SSC assessment.

	Statistical Analysis Plan	
FLU010	Final analysis	Final 3.0 of 15JUN2020

- Total days of fever = total number of days on which body temperature > 38°C
 - All time points (including unscheduled time points) from day 1 to day 11 will be considered, except for pre-challenge time points.
- Total mucus production (g) = (summed weight of all used bags + all used tissues + all returned clean tissues) - (summed weight of clean bags containing clean tissues)
 - Total mucus production will not be calculated for challenge cohorts 1 to 4 (due to problems with data collection for these cohorts).
 - Total mucus production will only be calculated in case all tissues were returned (sum of clean and used tissues returned should be 20 tissues for each bag).
 - Negative results for total mucus production within 2 SE of the mean result (within treatment group), will be set to zero.
- Local SSC score = arithmetic mean of local symptom items
Missing items will be handled as detailed in section 5.3.1
- General SSC score = arithmetic mean of general symptom items
Missing items will be handled as detailed in section 5.3.1

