Admission to study unit / discharge	Admission ¹		Confinement										Discharge		
Full Days Residence		x	x	x	x	x	x	x	x	x	x	x			
Safety Assessments															
Physical Exam	x													x	x
Symptom-Directed Physical Examination		x	x	x	x	x	x	x	x	x	x	x		x	
Vital Signs	x	x	x	x	x	x	x	x	x	x	x	x	x	x	x
Spirometry		x										x		x	
Peak Flow		x	x	x	x	x	x	x	x	x	x	x		x	
Supine 12-lead ECG ⁶		x				x								x	x
Pulse oximetry		x	x	x	x	x	x	x	x	x	x	x			
Drug / Alcohol Screen	x													x	
Urine Pregnancy Test	x													x	x
Biochemistry ^{4a}	x ¹			x						x				x	
Haematology	x ¹			x						x				x	
Symptom Score (Questionnaire) – b.i.d.			x	x	x	x	x	x	x	x	x	x	x ⁴		
Concomitant therapy - AEs/ SAEs	x	x		x						x				x	x
Study Agent Administration / Pharmacokinetic and Immunogenicity Assessments															
Viral Inoculation			x												
NP swabs samples for qualitative PCR testing - multiple viruses - (CPU Antwerp) ²	x											x			
NP swabs sample for viral load by qPCR (culture done if positive) – b.i.d. (after challenge)				x	x	x	x	x	x	x	x	x			
Tissue Collection for Mucus weights ⁷			x	x	x	x	x	x	x	x	x	x			
Blood sample for humoral immunogenicity (MNT) and Hemagglutination Inhibition (HI) assays ⁸	x ¹													x	
Blood sample for cellular immunogenicity assays PBMCs ⁹	x ¹													x	

Period 2	In-Clinic Confinement													Unscheduled Visit ³	Out-patient Day 28 ⁵ ±3
	Day -2	Day -1	Day 1	Day 2	Day 3	Day 4	Day 5	Day 6	Day 7	Day 8	Day 9	Day 10	Day 11		
Transcriptomics - whole blood collection (PAXgene® RNA)	x ¹⁰	x ¹⁰		x			x			x					x

¹ Admission to clinic is possible on Day -1, in which case Day -2 assessments may be performed on Day -1. Pre-challenge assessments may be performed on Day -2 or Day -1.

² Multiplex PCR tests are to be performed to determine whether participants are incubating other viruses at the time of inoculation. Participants with positive results should not enter the challenge group and could be offered to be part of one of the subsequent groups if their infection is cleared.

³ Assessments during Unscheduled Visits will be performed at the discretion of the Investigator

⁴ Symptom Score Questionnaire to be administered b.i.d. from Day 1 to Day 10 but only once prior discharge on Day 11

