
Prior and concomitant medications will be coded using the World Health Organization (WHO)_DRUG Dictionary.

9.1.2 *Efficacy Data*

A more detailed description of all efficacy analyses will be included in the trial's SAP, including planned supportive and sensitivity analyses, as well as methods for imputing missing data.

9.1.2.1 *PRIMARY ENDPOINT*

The trial's primary endpoint is a comparison of the viral shedding of influenza virus in MVA-NP+M1 versus placebo recipients following human challenge, as measured by the cumulative area under the curve (vAUC). Difference in vAUC, as measured and quantitated by log-transformed qPCR, will be evaluated using a Mann-Whitney U Test. AUC will be calculated using the trapezoidal rule. In case no viral load was detected, the \log_{10} viral load will be imputed.

Mean (\pm Standard Error (SE)) viral load over time will be summarized and presented graphically in \log_{10} scale by treatment group.

9.1.2.2 *SECONDARY ENDPOINTS*

The attack rate, defined as percentage of inoculated participants with at least two positive swabs as determined by qPCR, will be summarized in percentages and 95% confidence intervals (CIs) by treatment group. The difference between the two treatment groups will be compared by a Fisher's exact test.

Time to start, time to peak and time to cessation of viral shedding from virus inoculation and duration of viral shedding will be summarized by the Kaplan-Meier method. Differences between the treatment groups will also be tested using the log-rank test. Differences in peak between treatment groups will be tested using a Mann-Whitney U test.

The same analyses as performed for qPCR will be performed on quantitative culture.

Secondary endpoints include the rate of virologically confirmed ILI (defined as a respiratory or flu-like symptom occurring on two consecutive days, along with a positive PCR or culture) measured between groups. Incidence of laboratory-confirmed influenza will be compared between vaccine groups using Fisher's Exact Test.

Another key secondary endpoint of relevance to the biologic effect of this vaccine will be the comparison of the symptom severity as an AUC. This endpoint takes into account both the severity and the duration of symptoms. Total and individual symptom scores from Day 1 to Day 11 post-challenge, will be compared by AUC using a Mann-Whitney U test.

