2. EFFICACY AND IMMUNOGENICITY ANALYSES

2.1 EFFICACY

2.1.1 *Available data*

Nasal swabs for influenza virus are collected twice a day (at least 8 hours apart) from Day 2 to Day 10 following intranasal challenge, which are tested for influenza using quantitative polymerase chain reaction (qPCR) and culture. Culture is only done for positive qPCR samples.

The following symptoms of influenza-related infection will be collected twice a day (except for lymphadenopathy, which will be collected once a day only) from Day 1 to Day 11 of challenge on a symptom score card (SSC):

- Local symptoms:
 - Nose (4): nasal congestion (blocked nose), runny nose, sneezing frequency, sinus pressure/pain or facial pain
 - Throat (2): sore throat, difficulty swallowing
 - Eyes (3): tearful/watery eyes, painful eyes, aversion to light
 - Chest/respiratory (3): dry cough, productive (wet) cough, difficulty breathing/tight chest
- General symptoms:
 - Gastrointestinal (4): nausea, stomach ache, vomiting, diarrhoea
 - Body/systemic (12): dizziness, head congestion, headache, muscle aches, feverish, chills or shivering, lack of appetite, felt cold, sweating, tiredness/weakness, sleeping more than usual, lymphadenopathy
 - The following symptoms will only be questions if at least 2 other symptoms with grade 2 or higher are present: nausea, stomach ache, vomiting, diarrhoea, tiredness/weakness, sleeping more than usual.

Each symptom's severity is graded from 0 (absent) to 3 (grade 3 - severe).

Additionally, the SSC also contains the question whether the subject feels well enough to go to work today (yes/no).

Oral body temperature is assessed daily during confinement as part of the vital signs evaluation. During this same period, tissue collection is planned daily to measure daily mucus production.

	Statistical Analysis Plan	
FLU010	Final analysis	Final 3.0 of 15JUN2020

2.1.2 *Endpoints and derivation rules*

2.1.2.1 *PRIMARY ENDPOINT*

Primary endpoint is the viral area under the curve (vAUC) based on the qPCR values. AUC will be calculated using the linear trapezoidal rule, by summing all individual trapezoids, which will be calculated as follows:

$$AUC_{t_i-t_{i+1}} = 1/2 * (L_i + L_{i+1}) * (t_{i+1} - t_i).$$

Where:

- L_i is the log-transformed viral load concentration at time point t_i .
- All time points (including unscheduled time points) from day 2 to day 10 will be considered.
- AUC will be calculated in hours, using actual datetimes of qPCR assessments.

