- Duration of viral shedding (hours) = (datetime of first negative swab following the last positive swab - datetime of first positive of two positive swabs within 2 consecutive days)/(60*60)
 - Duration will be rounded as detailed in section 5.3.4
 - All time points (including unscheduled time points) from day 2 to day 10 will be considered.
 - Subjects not having at least two positive swabs (within 2 consecutive days) will be excluded from this analysis (duration of viral shedding not calculated).
 - The end of viral shedding is defined as two consecutive negative swabs not followed by a positive swab. If this does not occur, the end of viral shedding will be set to the last viral load assessment.
 - This endpoint will be derived for both qPCR and culture
- vAUC based on culture values will be derived following the same rules as for the primary endpoint

	Statistical Analysis Plan	
FLU010	Final analysis	Final 3.0 of 15JUN2020

- Rate of virologically confirmed ILI: virologically confirmed ILI is defined as having a positive swab and a respiratory or flu-like symptom occurring on two consecutive days
 - A positive swab is defined as a positive qPCR.
 - All time points (including unscheduled time points) from day 2 to day 10 will be considered.
 - Positive swab and flu-like symptom have to occur on the same two consecutive days.
 - Respiratory or flu-like symptom can be any of the following signs or symptoms collected on the SSC: runny nose, sneezing frequency, sinus pressure/pain or facial pain, sore throat, difficulty swallowing, teary/watery eyes, painful eyes, aversion to light, dry cough, productive (wet) cough, difficulty breathing/tight chest, feverish, chills or shivering, sweating, lymphadenopathy
- Overall SSC AUC
 - AUC will be derived following the same rules as for the primary endpoint and rounded as detailed in section 5.3.4
 - SSC AUC will be calculated using the overall SSC score
 - Overall SSC score = arithmetic mean of all items
 - As lymphadenopathy is assessed only once a day, the value collected for that day will be used for both the AM and PM assessments in the calculation of SSC score.
 - Missing items will be handled as detailed in section 5.3.1

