5.3 IMPUTATION AND ROUNDING RULES

5.3.1 *Missing values*

As culture is only done for positive qPCR values, missing culture results with a qPCR value 'not detected', will be considered as zero (log10).

	Statistical Analysis Plan	
FLU010	Final analysis	Final 3.0 of 15JUN2020

For the calculation of AUCs, the following rules will be used to impute missing values:

- Intermittent missing values will be interpolated. This is implicitly done when using the linear trapezoidal rule.
- In case of trailing missing values, a triangle will be calculated to estimate the area between the timepoint of the last non missing value and the last scheduled assessment, which will be assumed to have a zero value.
- In case of leading missing values, a triangle will be calculated to estimate the area between the first non missing assessment and the first scheduled assessment, which will be assumed to have a zero value.
- In case of trailing missing values with no assessment datetime, the last scheduled assessment datetime will be imputed with challenge datetime + 10 days + 12 hours (for viral load) or + 11 days (SSC)
- In case of leading missing values with no assessment datetime, the first scheduled assessment datetime will be imputed with challenge datetime – 1 min + 1 day (viral load) or with challenge datetime – 1 min (SSC)

Overall/Local/General SSC score will only be calculated if sufficient signs and symptoms are available for each body system: 3/4 nose; 1/2 throat; 2/3 eyes; 2/3 chest/respiratory; 3/4 gastrointestinal and 8/12 body/systemic. Symptoms that are questioned if at least 2 other symptoms with grade 2 or higher are present should only be considered as missing if the condition is met and no value is available.

In case percentage of missing data exceeds 5% for qPCR viral load or for overall SSC, a sensitivity analysis will be done for the AUC based endpoints by using a placebo-based multiple imputation which assumes that all missing viral load concentrations/signs and symptom scores are missing not at random (MNAR). This approach can be considered conservative as subjects from the active treatment arm would adopt the outcome model estimated from the placebo arm.

For the safety analysis, no imputation will be done of missing values (i.e. observed cases analysis).

5.3.2 *Handling partially or completely missing datetimes in calculations*

Partially missing datetime of event will be imputed as follows for the calculation of AUC:

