9.2 INFLUENZA SYMPTOM SCORE CARD OF FLU010 - BE-80-1800488

Group	Subject	Screening number:
-------	---------	-------------------

^a Fill in the SSC twice daily, at approximately 12h intervals (AM and PM) starting on Day1.
^b Score the severity of the symptoms with 0: absent, 1: mild, 2: moderate or 3: severe – each field should be filled out.
^c For the current score of a symptom, fill in the worse severity during the period between 2 SSC's.

	Day1		Day2		Day3		Day4		Day5		Day6		Day7		Day8		Day9		Day10		Day11
	AM	PM	AM	PM																	
Time point of collection (HH:MM)																					
Medication taken during the last 12h?	Y/N	Y/N	Y/N	Y/N																	
Feel well enough to go to work today?	Y/N	Y/N	Y/N	Y/N																	
Respiratory tract (upper + lower)																					
Blocked nose																					
Runny nose																					
Sneezing frequency																					
Sinus pressure/pain or facial pain																					
Sore throat																					
Difficulty swallowing																					
Teary/ watery eyes																					

Statistical Analysis Plan

FLU010

Final analysis

Final 3.0 of 15JUN2020

	Statistical Analysis Plan													
FLU010	Final analysis										Final 3.0 of 15JUN2020			

Interviewer initials															
Investigator initials															
Lymphadenopathy?															
Moderate/ severe sign/symptom of lower respiratory tract involvement?	Y/N														

	Statistical Analysis Plan	
	Final analysis	Final 3.0 of 15JUN2020

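### Time to start and time to peak of symptoms do not exclude the pre-inoculation symptom card, and the SAP contradicts itself on the time window for the symptom-score AUC

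*SAP*

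**What the plan says.** **When cards are completed.** The protocol's challenge schedule says "Symptom Score Questionnaire to be administered b.i.d. from Day 1 to Day 10 but only once prior discharge on Day 11", and the card in SAP 9.2 says "Fill in the SSC twice daily, at approximately 12h intervals (AM and PM) starting on Day1". SAP 5.3.1, which supplies times for missing AUC endpoints, sets the first scheduled card "with challenge datetime – 1 min (SSC") and the last at challenge plus 11 days.

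**Timing endpoints.** SAP 2.1.2.3 defines onset as "Time to start of symptoms (hours) = (datetime of first of two non-zero overall SSC scores within 2 consecutive days - challenge datetime)/(60*60"). Time to peak is the time of the highest overall SSC score, again measured from challenge, and ties go to the earliest card. Neither entry has a day window or a pre-challenge exclusion. Peak symptoms and duration of symptoms, in the same list, each carry the line "Pre-challenge time points will not be considered". Days of fever has an equivalent exclusion. Protocol 9.1.2.3 counts symptom times from inoculation.

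**Symptom AUC.** For the overall SSC AUC, SAP 2.1.2.2 says "AUC will be derived following the same rules as for the primary endpoint". One of those rules, in SAP 2.1.2.1, is "All time points (including unscheduled time points) from day 2 to day 10 will be considered". Protocol 9.1.2.2 instead names "Total and individual symptom scores from Day 1 to Day 11 post-challenge" as the scores to be compared by AUC.

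**The concern.** The onset and peak rules can select a card filled in before the participant was exposed to virus. The resulting time is negative, and a survival analysis that starts its clock at inoculation has no valid place for it. The SAP does not say whether such a value would be dropped or counted as an immediate event; neither describes influenza onset. Related endpoints would also disagree within one participant: the start used for duration could differ from the reported time to start, and the reported time to peak could belong to a card that the peak value excludes.

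The AUC matters more by rank. Protocol 9.1.2.2 treats symptom AUC as a key secondary endpoint, and SAP section 8 flags its table for the topline results. If two sections of the SAP imply different windows, the programmer has to choose. Under SAP 1.7 only the primary endpoint tables are independently programmed, so a wrong choice here is less likely to be caught.

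**Working it through.** The plan states no figure on this point. The check compares the rules and then does schedule arithmetic.

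**1. Is the first card pre-inoculation?** Four places agree that it is.
- SAP 5.3.1 times the first scheduled card at challenge minus 1 minute.
- The protocol schedule lists the symptom score under safety assessments, and protocol 7.1.2.2 places inoculation after those.
- The repeated-measures model in SAP 2.1.3 analyses SSC change from baseline, and SAP 5.2.2 defines challenge baseline as the last value before inoculation.
- The exclusions written for peak and duration presuppose that such cards exist.

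**2. Which symptom endpoints exclude it?**

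| Endpoint (SAP 2.1.2.3) | Pre-challenge excluded? |
|---|---|
| Peak symptoms | Yes |
| Duration of symptoms | Yes |
| Days of fever | Yes |
| Time to start | No |
| Time to peak | No |
| Time to cessation | No |

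SAP 5.2 defines phases and baselines. It contains no general rule restricting these derivations to the challenge phase.

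**3. How little is needed?** SAP 2.1.1 lists 4 + 2 + 3 + 3 + 4 + 12 = 28 items. One grade 1 item gives an overall score of 1/28 = 0.036. If the 6 conditionally asked items are left out of the mean, it is 1/22 = 0.045. Either is non-zero. The SAP's definition of within 2 consecutive days allows zero cards between the two non-zero ones, so Day 1 AM can pair with any card up to Day 2 PM.

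**4. What the rule returns.** Nominal clock: Day d AM = 24 × (d − 1) h, PM = 12 h later. Suppose the first card is completed 60 minutes before challenge (−1 h).
- *Participant A:* non-zero on Day 1 AM (−1 h), Day 2 PM (36 h) and Day 3 AM (48 h), zero otherwise. As written, onset is −1.0 h. With the exclusion it is 36 h, a shift of 36 − (−1) = 37 h.
- *Participant B:* non-zero on Day 1 AM (−1 h) and Day 2 PM (36 h) only. Time to start records an event at −1.0 h. Once the first card is ignored, peak and duration have no qualifying pair and omit the participant. Time to cessation still includes the participant, with an event at Day 3 AM, 48 h.

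After rounding to one decimal, a card 5 minutes before challenge gives −0.1 h.

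**5. How often?** The documents give no rate of non-zero first cards. As a labelled assumption, 5% to 15% of the 134 challenged gives 134 × 0.05 = 6.7 to 134 × 0.15 = 20.1, or about 7 to 20 people. Under that assumption this is an upper bound, because a second non-zero card by the end of Day 2 is also required.

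**6. SSC AUC window.** Scheduled cards: 2 × 10 + 1 = 21.

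| Reading | Cards | Nominal span |
|---|---|---|
| Day 2-10 (literal cross-reference) | 2 × 9 = 18 | 24 to 228 h = 204 h |
| Day 1-11 (protocol 9.1.2.2), first card included | 21 | 0 to 240 h = 240 h |
| Day 1-11, first card left out | 20 | 12 to 240 h = 228 h |

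The literal reading omits Day 1 AM, Day 1 PM and Day 11: 240 − 204 = 36 h, and 36/240 = 15% of the nominal hours. The SAP 5.3.1 anchors run from −1 minute to 11 × 24 = 264 h. They include Day 1 and end 24 h after the nominal Day 11 morning card, so they cannot be reconciled with Day 2-10.

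**The case against.** **On the timing endpoints.** The intent is clear: the protocol counts from inoculation, and the SAP's challenge phase begins at the challenge time. Time to peak can naturally be read as the time of the peak just defined, which already excludes pre-challenge cards. Even on the literal reading, a pre-challenge card is selected only if its score equals or exceeds every later one. Protocol 4.3 keeps out participants with influenza-like symptoms or fever at admission, or a positive viral PCR. All of this stands as to intent and frequency. It does not supply the missing exclusion: the SAP states it for neighbouring endpoints and not for these two, and one mild item need not amount to influenza-like illness.

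**On the AUC.** A reader might infer that the symptom AUC fails to cover Day 1 to Day 11 and so loses 15% of its window. The documents do not support that. SAP 5.3.1 gives the SSC its own AUC anchors, which make no sense under Day 2-10, and SAP 2.1.1 collects cards from Day 1 to Day 11. The cross-reference also cannot be taken literally in full, because the primary-endpoint rules refer to log viral load and qPCR sampling times. The 15% is a share of nominal hours under one contested reading; it is not a measured loss of AUC or of power.

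**On direction.** A reader might also infer bias between arms. Allocation is randomised and those recording symptoms are blinded, so there is no reason to expect the error to favour either arm.

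**Conclusion.** The omission in time to start is real: as written, the rule can return onset before inoculation, contrary to the protocol's time origin and to the start used for duration. Time to peak has the same gap, but it takes effect only when a pre-challenge score is at least as high as every later score. Both endpoints are exploratory, the primary endpoint is untouched, and the likely consequence is noise. The frequency is unknown; the 7 to 20 of 134 shown above rests on an assumed 5% to 15% and is an upper bound under that assumption. Time to cessation cannot itself be negative, because a qualifying pair includes at least one post-challenge card; only its qualifying population can differ from that for peak and duration.

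For the SSC AUC the result is an unresolved contradiction within the SAP, with 18 or 21 scheduled cards depending on which section is followed. The weight of the text favours Day 1 to Day 11. These conclusions assume that the first card is completed before inoculation, as the documents indicate, and they use nominal rather than actual card times.

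**What to change.** - In SAP 2.1.2.3, add "Pre-challenge time points will not be considered" to time to start and time to peak of symptoms. Adding it to time to cessation is optional; it would give that endpoint the same qualifying population as peak and duration.
- In SAP 2.1.2.2, state that the SSC AUC covers Day 1 to Day 11 and that this overrides the Day 2-10 rule inherited from the primary endpoint.
- In the same place, say whether the pre-challenge card serves as the time-0 value (21 scheduled cards) or is left out (20).
- Check the end anchor in SAP 5.3.1 against the Day 11 card, since the two differ by a nominal 24 h.

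The cost is a few lines of SAP text and the matching derivation code. No data collection changes.

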2.2 SECONDARY OBJECTIVES

Secondary objectives are to determine:

- The incidence in each group (MVA-NP+M1 and saline Placebo) of laboratory-confirmed influenza (qPCR or culture) (and time to start; time to peak and duration of qPCR and quantitative culture results)
- The attack rate, defined as percentage of inoculated participants with at least two positive swabs as determined by qPCR
- Total AUC for total symptom score for MVA-NP+M1 vs. Placebo
- Total days of fever for MVA-NP+M1 vs. Placebo
- Total mucus weight for MVA-NP+M1 vs. Placebo
- Correlation of T cell responses (as defined by ELISpot assay) to the primary endpoint, symptom scores, and influenza incidence
- Safety of MVA-NP+M1 vaccination
- Safety of H3N2 challenge in the setting of MVA-NP+M1 vaccination

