1.2 STUDY DESIGN

This is a randomized, single-centre, double blind study. The study screens healthy volunteers and only enrolls those with microneutralisation test (MNT) < 20. The study consists of an outpatient vaccination phase, and at least 6 weeks later an inpatient challenge phase.

155 participants are randomized 3:2 to receive either MVA-NP+M1 (N=93) or Placebo (N=62) by intramuscular injection in the non-dominant arm deltoid. Vaccination-related local and systemic symptoms are followed by participant-directed diary cards for 7 days, and unsolicited adverse events are followed throughout the study from consent signature.

A total of 80 participants from the MVA-NP+M1 group and 54 from the saline Placebo group are challenged. Participants enter the quarantine facility on Day -2 or Day -1 and are discharged on Day 11. Participants receive a single intranasal administration of the H3N2 challenge agent via nasal spray. Challenge-related local and systemic symptoms are followed up to twice a day using investigator-directed symptom score cards for 11 days.

The schedule of assessments is in section 9.4.1 for the vaccination period and in section 9.4.2 for the challenge period.

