4.6 EXPOSURE TO STUDY DRUG AND TREATMENT COMPLIANCE

4.6.1 *Available data*

Vaccination occurs in 7 cohorts, with an approximate 3-week interval. Subjects are vaccinated only once, but for each cohort, vaccination can occur on multiple scheduled dates. Challenge occurs at least 6 weeks later, in 8 cohorts, with a 3-week interval. In case the challenge cohort is different from the vaccination cohort, this is documented in a structured comment in the clinical database.

4.6.2 *Derivation rules*

Time between vaccination and challenge will be calculated in days as date of challenge - date of vaccination + 1

	Statistical Analysis Plan	
FLU010	Final analysis	Final 3.0 of 15JUN2020

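### The SAP's rule for negative mucus totals does nothing unless an arm mean is below 2 SE and then works by arm, and one incomplete bag voids a participant's total with no sensitivity analysis (minor)

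*SAP*

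**What the plan says.** SAP 2.1.2.3 derives total mucus production as the summed weight of everything returned minus the summed weight of the clean bags with their tissues. Three rules follow.

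- Cohorts: "Total mucus production will not be calculated for challenge cohorts 1 to 4", because of problems with data collection. SAP 4.6.1 gives the number of cohorts: "Challenge occurs at least 6 weeks later, in 8 cohorts, with a 3-week interval".
- Completeness: "Total mucus production will only be calculated in case all tissues were returned", with the explanation that the "sum of clean and used tissues returned should be 20 tissues for each bag".
- Negative totals: "Negative results for total mucus production within 2 SE of the mean result (within treatment group), will be set to zero".

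SAP 2.1.3 compares the arms by t-test, or by Mann-Whitney U test if normality or equal variance fails. SAP 5.3.5 keeps all measured values, so a negative total that is not zeroed enters the analysis as it stands. The missing-data provisions in SAP 5.3.1 cover the AUCs and the symptom scores but not mucus weight.

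The endpoint's status is mixed. Protocol 2.2 lists "Total mucus weight for MVA-NP+M1 vs. Placebo" as a secondary objective, and SAP 1.1 repeats it. Protocol 9.1.2.3, SAP 2.1.2.3 and the table list in SAP 8.1 analyse it as exploratory.

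**The concern.** A rule for negative weights should deal with weighing error around zero. This one is centred on the arm mean and uses the standard error, which describes the precision of the mean and not the spread of individual totals. It therefore looks unlikely to reach the values it was written for. Because the mean and SE are taken within treatment group, data handling also depends on the arm, for no evident gain.

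The completeness rule is strict in a way that the rest of the SAP is not. AUCs are interpolated over gaps, symptom scores tolerate missing items, and the AUC endpoints get a multiple-imputation analysis if more than 5% of the qPCR or symptom data are missing. For mucus, one short bag removes the participant's whole stay, and no analysis shows whether that matters. The table is nevertheless labelled ITT. At stake is how far a reader can rely on an endpoint to which at most part of the ITT set contributes.

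**Working it through.** The documents give no mean, SD, power or count of incomplete returns for mucus weight, so there is no stated figure to reproduce.

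**1. When can the negative-value rule act?** For an arm with mean m > 0, SD s and n totals, SE = s/√n and the window is m ± 2 SE. It contains a negative number only if m < 2s/√n, that is, if CV = s/m > √n/2.

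| n in arm | CV needed |
|---|---|
| 22 | 2.35 |
| 27 | 2.60 |
| 32 | 2.83 |
| 40 | 3.16 |

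For example, with an assumed mean of 20 g and SE of 3 g the window is 14 to 26 g, and no negative total is touched.

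**2. What does it do when it acts?** It reaches down to m − 2 SE and no further, so the most negative totals stay. The limit also differs by arm. Assume the same mean (1 g) and SD (3 g) in both arms, with 32 and 22 totals:

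- vaccine: 1 − 2 × 3/√32 = 1 − 1.06 = −0.06 g
- placebo: 1 − 2 × 3/√22 = 1 − 1.28 = −0.28 g

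A total of −0.2 g is then zeroed in the placebo arm and kept in the vaccine arm. With equal SDs and 3:2 allocation the placebo SE is √1.5 = 1.22 times the vaccine SE, so the windows differ even with no vaccine effect.

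**3. How often?** A simulation (20,000 runs per scenario, arms of 32 and 22) drew lognormal mucus weights, a share of true zeros, and normal weighing error. All inputs are assumptions. Mean and CV refer to participants who produce any mucus.

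| Mean, CV | Error SD | True zeros | Totals negative | Negatives set to zero |
|---|---|---|---|---|
| 10 g, 1 | 1–3 g | 20% | 10–15% | 0.0–0.2% |
| 5 g, 1.5 | 3 g | 20% | 25% | 0.6–2.8% |
| 0.5–2 g, 1–1.5 | 3 g | 30–50% | 37–47% | 7–28% |

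With SD in place of SE in the rule, about 96% to 100% of negatives would be zeroed. That may be what was meant, but the SAP does not say so.

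**4. How many participants remain after the cohort exclusion?** SAP 1.2 plans 80 + 54 = 134 challenged, and the protocol synopsis allows up to 20 per cohort.

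- Cohorts 1 to 4 full: 134 − 4 × 20 = 54 (40%), about 32:22.
- Equal cohorts: 134/2 = 67 (50%), 40:27.
- Only 120 challenged (the worst case in SAP 1.3) and cohorts 1 to 4 full: 120 − 80 = 40, or 24:16.
- Small early cohorts: more than 67, up to 4 × 20 = 80 if the limit of 20 holds.

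The standardised difference detectable with 80% power at two-sided 0.05 is (1.960 + 0.842) × √(1/n1 + 1/n2): 0.49 at 80:54, 0.70 at 40:27, 0.78 at 32:22 and 0.90 at 24:16.

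**5. What could the tissue rule remove?** If each tissue is returned independently with probability q, P(complete) = q^(20 × bags). The number of bags is not stated. Protocol 7.2.8 has two recordings a day and SAP 2.1.1 describes daily collection, so 10 to 21 bags (200 to 420 tissues) is assumed.

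| q | 10 bags | 21 bags |
|---|---|---|
| 0.9999 | 0.98 | 0.96 |
| 0.999 | 0.82 | 0.66 |
| 0.995 | 0.37 | 0.12 |
| 0.99 | 0.13 | 0.015 |

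The loss could be anywhere from about 2% to 98%, so the documents do not settle it.

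**The case against.** The strongest defence is that a rule that never fires does no harm. If both arm means exceed 2 SE, every negative total is kept as measured in both arms, which is itself an acceptable way to handle them. A negative difference between two summed weights can be plain weighing error. Under the Mann-Whitney fallback, zeroing a few low values mainly creates ties at the bottom. All of this stands, and no effect on the estimate or p-value has been shown. The rule is also mechanical, and the mucus table is not flagged for the topline results, so nothing shows that the derivation is needed before unblinding.

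A reader might infer more than the documents support.

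- *That the rule can never act.* It can, when an arm mean is below 2 SE. Differential handling of the arms arises only then.
- *That the tissue rule selects on the outcome, because heavy users lose more tissues.* Clean and used tissues are counted together, 20 per bag, so everyone with the same number of bags has the same number at risk. Heavier users are more exposed only if they get extra bags or lose used tissues more often, and neither is documented. Quarantine staff collect the tissues.
- *That these two rules make the sample small.* The negative-value rule removes nobody, and the loss from the tissue rule is unknown. The documented loss is cohorts 1 to 4. It is defined by cohort, attributed to data-collection problems, and not recoverable by a change in derivation.

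**Conclusion.** The point holds as a minor one. That the negative-value rule is inert unless an arm mean is below 2 SE is algebra and needs no assumption beyond a positive mean. That it leaves the most negative totals and uses arm-specific limits follows directly from its wording. How often it would act depends on assumed means, CVs and weighing error.

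That one incomplete bag voids a whole total, with no partial total or sensitivity analysis, is also plain from the text. The 54 to 67 contributors before that rule assume 134 challenged and either full early cohorts or equal ones. Bias between arms, or by amount of mucus, is possible but not shown. The SAP analyses the endpoint as exploratory, although it answers a protocol secondary objective, so the effect on the trial's conclusions is small.

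**What to change.** 1. Delete the 2-SE rule. Apply one rule to every negative total in both arms without reference to treatment: either keep all signed values or set all negatives to zero.
2. Keep total mucus weight as the endpoint. Add a sensitivity analysis of mean net weight per complete bag (or per day) in all participants of the usable cohorts, provided that weights were recorded per bag.
3. Report by arm how many participants contribute a total, why the others do not, and the number of complete bags.

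The cost is a few lines of SAP text and the reprogramming of one derivation from data already collected. The downside is that participants contribute different numbers of bags to the sensitivity analysis. If incompleteness did track the amount of mucus, dropping incomplete bags would move that selection to bag level, which is one reason to report the counts. None of this recovers cohorts 1 to 4.
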